ideation or behaviors (assessed by Patient health questionnaire- 9, PHQ-9) (Kronke, Spitzer, Williams, Lowe, 2010); (5) present excessive drinking problems scoring 19 or higher on Alcohol Use Disorders Identifications Test, AUDIT (Saunders et al., 1993). Medication use is permitted only if the dosage was constant in last month and it will remain the same during the trial. All eligible participants must fill in and return a detailed informed consent before starting the trial.

The inclusion and exclusion criteria are in accord to those used in the literature about ICBT intervention on PTSD problems (Ciuca et al., 2016; Ehring, Ehlers, Cleare, Glucksman, 2008; Ivarsson et al., 2014; Wild et al., 2016).

Recruitment

Participants will be recruited from the general population. The participants will be Native Romanian speakers with Posttraumatic Stress Disorder (n=108). They will be recruited by recommendation from local specialists in mental health (psychiatrist, psychotherapist) and via media (Facebook advertise, TV news, radio news, internet advertisements and social media), advertising delivered in hospitals, organizations for victims of domestic violence and sexual abuse, emergency rooms and direct recommendations made by mental health practitioners.

Procedure

The participants can contact the study administration team at any time through using email or messaging on the platform. Participation in the study is voluntary. Participants can withdraw anytime from the study without any consequences. They will receive an information sheet detailing psychological treatments available, according to symptom severity assessed in the evaluation phase or upon contacting study administration team.

We will have diagnostic interviews and self-reports assessments as it follows: screening (T0), preintervention assessment (T1), middle intervention assessment (T2) after 5 weeks of study begins, post intervention assessment (T3) and a 3 months follow-up assessment (T4) (See **Figure 1** for a detailed overview of the study). For the evaluation phase we will use diagnostic interviews conducted face to face or by telephone and self-report assessment. Self-report assessment will be conducted using a secure online-based assessment system, incorporated in the platform. The participants' symptoms will be monitored every week. All the procedures from the study will be congruent with the generally accepted standards of ethical practice.

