The effect size for iCBT intervention for PTSD is considered to be small to medium (Kuester, Niemeyer & Knaevelsrud, 2016; Lewis et al., 2019; Sibrandij, Kunovski & Cuijpers). Take this information in consideration we expected an effect size of .60. Based on this effect size, a power of .80 and a level alpha of 0.05 we would need 45 participants in each condition for testing the two tails hypothesis. This recommended sample size has been increased to accommodate an attrition rate of 20%. Thus, the study aims to achieve a total sample of 108.

Statistical analysis

All statistical analyses will be performed using the IBM SPSS Statistics version 20. The aim analysis will be conducted on intention-to-treat samples. We will use a linear mixed effects models approach with full information maximum likelihood estimation. This approach was recommended since it uses all available data and can handle missing data appropriately (Gueorguieva & Krystal, 2004; Meyer et al., 2015; Pond, 2011). The approach emphasizes the assumption that data are randomly missing and does not assume that missing data remain stable as in the last-observation-carried-forward (LOCF) approach (Blankers, Koeter & Schippers, 2010; Meyer et al., 2015). Significance testing of dichotomous data such as diagnostic status will be conducted with chi-square tests. Calculation of within and between- groups effect sizes (Cohen d) will be based on the pooled standard deviations. Regression analyses will be used to identify predictors of treatment outcome. Moderation and mediation analysis will be conducted with multiple regression models, using the PROCESS macro for SPSS (Hayes, 2017), a computational technique that can compute both simple and complex moderation and mediation models. Effect sizes for significant effects will be indicated by Cohen's d.

Consistent with recommendations from CONSORT (Schulz, Altman, Moher, 2011) and SPIRIT (Chan et al., 2013) we mention our intention to perform secondary analyses for minimal treatment users, defined as participants that complete at least 5 of recommended modules and use the intervention program for at least 80 minutes. This definition is based on the specific of our intervention program and the criteria used in other studies (Ciuca et al., 2011; Meyer et al., 2015; Ivarsson et al., 2014).

Discussion

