We expect that our program PAXPTSD to be effective for PTSD global severity symptom as well as for subscale for re-experiencing, avoidance, changes in mood and cognitions and hyperarousal. We expect that these results to be maintained (3 months follow-up). These results will be in line with the literature on effectiveness of Internet-delivered cognitive behavior therapy for PTSD showing that Internet-delivered cognitive behavioral interventions are more effective than waitlist control group (Sijbrandij, Kunovski, Cuijpers, 2016). We expect that the effect size for our study to be medium to large and to be in line with other ICBT programs. Internet-based treatments also resulted in moderate to large effects for other disorders such as anxiety (Cuijpers et al., 2009; Reger & Gahm, 2009; Tulbure, 2011) and small to moderate ones for depression (Andersson & Cuijpers, 2009; Cowpertwait & Clarke, 2013; Richards & Richardson, 2012; So et al., 2013). ICBT that provided support resulted in a large effect, whereas a medium effect was obtained without support. Because there are no firm conclusions about the role of the therapist

in ICBT, we decide to keep to minimum the psychotherapist implication. In our study the psychologist will discuss the results of the evaluation in a kickoff meeting as well as offer feedback, respond to question, monitor the progress and offer reminders every week.

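### The planned total of 108 covers attrition of 16.7%, not the stated 20%, because 90 was multiplied by 1.2 instead of divided by 0.8; separately, the protocol describes its expected effect in conflicting words

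*Protocol*

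**What the plan says.** The Sample size section sets out the calculation in three steps.

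- **Effect.** It characterises earlier results: "The effect size for iCBT intervention for PTSD is considered to be small to medium". In view of this, "we expected an effect size of .60".
- **Number needed.** With "a power of .80 and a level alpha of 0.05", it concludes that "we would need 45 participants in each condition" "for testing the two tails hypothesis".
- **Attrition.** That number "has been increased to accommodate an attrition rate of 20%. Thus, the study aims to achieve a total sample of 108".

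The Recruitment section repeats the total: "Native Romanian speakers with Posttraumatic Stress Disorder (n=108".

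Two other places describe the size of the effect. The Discussion says: "We expect that the effect size for our study to be medium to large". The Introduction reports moderate to large effects against passive control, and the comparator in this trial is a waiting list.

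**The concern.** An attrition rate applies to the people enrolled, so an allowance for it is made by dividing the number needed by the retained fraction. Multiplying by one plus the rate gives too few. Here the stated total matches the multiplication exactly. The protocol therefore claims a property of its sample size (45 per arm left after 20% loss) that its own figures do not deliver. The allowance is the stated reason for enrolling 108 and not 90, and anyone judging observed dropout against the plan will rely on it.

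The second matter is one of wording. The section that fixes .60 describes the literature in one way and the Discussion describes the expected effect in another, so the reader cannot tell what .60 rests on.

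**Working it through.** **Inputs, all from the Sample size section:** standardised effect 0.60, two-sided alpha 0.05, power 0.80, 45 per arm (90 in total, equal allocation), attrition 20%, planned total 108.

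**Step 1. Reproduce the 45 per arm.**
- Normal approximation: n = 2(1.960 + 0.842)²/0.60² = 43.6, rounded up to 44.
- Two-sample t-test (noncentral t): n = 44.6, rounded up to 45. This matches the protocol.
- A one-sided test would need about 35 to 36 per arm, so the two-sided statement fits as well.

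**Step 2. Reproduce the 108.**
- 90 × (1 + 0.20) = 108, which matches exactly.
- 90 / (1 − 0.20) = 112.5, so 113 in total. Per arm, 45/0.8 = 56.25, so 57 per arm and 114 in total.
- Starting from the normal-approximation figure of 44 per arm does not recover 108 either: 88/0.8 = 110. The protocol in any case states 45.

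**Step 3. What 108 delivers.**
- At 20% attrition: 108 × 0.8 = 86.4 completers, or 43.2 per arm.
- Largest loss that still leaves 90: 1 − 90/108 = 16.7% (18 participants, 9 per arm).
- Shortfall against the correct total: 113 − 108 = 5, or 114 − 108 = 6 with equal arms.

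**Step 4. Effect on power (two-sample t-test, d = 0.60, two-sided 0.05).**

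| Per arm analysed | Power |
|---|---|
| 45 (the stated requirement) | 80.4% |
| 43.2 (108 less 20%) | 78.7% |
| 43 (whole participants) | 78.5% |

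With 43 per arm, the effect detectable with 80% power is 0.61.

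**Step 5. The descriptions of the effect, side by side.**
- Sample size: small to medium for iCBT in PTSD, leading to .60.
- Discussion: medium to large expected for this trial.
- Introduction: moderate to large against passive control.
- Table 1, ICBT rows with a waiting-list comparator: 11 rows. Seven lie wholly above 0.60 (values from 0.67 to 1.50) and four lie below it (0.31, 0.46, 0.55 and 0.57–0.59).

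The Sample size and Discussion descriptions do not agree. The figure .60 sits comfortably with the Discussion, the Introduction and the waiting-list rows of Table 1. It is the adjective in the Sample size section that is out of line.

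**The case against.** **The slip hardly matters.** This is largely right. It costs about two participants per arm and less than two percentage points of power. It does not make the attrition statement true.

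**The completer count is not the power of the planned analysis.** This also stands. The Statistical analysis section plans an intention-to-treat mixed model with full-information maximum likelihood, and Table 2 schedules the PDS-5 before, during and after treatment and the PCL-5 weekly. Participants lost before the end would still contribute data, so a t-test on completers is a conservative proxy. As an illustration, with pre-post correlations that are assumed because the protocol gives none, baseline adjustment with 43 per arm at d = 0.60 gives power of about 82% (r = 0.3), 85% (r = 0.4) or 89% (r = 0.5). But the protocol sized the trial on a number per condition and then added an allowance for attrition, and on that basis the allowance is wrong.

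**A reader might infer that the protocol misstates the power of the trial.** It does not. It states .80 for 45 per arm, which is correct, and states no power for 108. Only the attrition allowance is misstated.

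**A reader might also infer that the trial is badly underpowered, because .60 exceeds a small-to-medium effect.** Power with 43 per arm would indeed be 63% at d = 0.50 and 45% at d = 0.40. But that reading takes one phrase literally against the Discussion, the Introduction and most of the waiting-list rows in Table 1. It also needs a cut-off that the protocol does not set: .60 lies above medium if medium means the point 0.5, and within it if medium means a band from 0.5 to 0.8. The documents do not support the inference.

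**Conclusion.** The attrition point holds on the protocol's own figures: 108 covers 16.7% attrition, not 20%, and is 5 to 6 participants short of what the stated allowance requires. This assumes that attrition is a proportion of those enrolled and falls equally on the two arms. The practical loss is small: power of about 79% at d = 0.60 by a two-sample t-test on completers, and possibly no shortfall under the planned mixed model.

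The effect-size point holds only as a conflict of wording between the Sample size section and the Discussion. Nothing in the protocol shows that .60 is too high, and whether the cited meta-analyses support the small-to-medium description cannot be checked from the protocol.

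**What to change.** 1. **Sample size section.** Keep 108 and replace the attrition statement with wording such as: *N = 108 retains 45 per arm with attrition up to 16.7%; with 20% attrition (about 43 completers per arm), power for a two-sample t-test at d = 0.60 is about 79%. The planned mixed model uses partial data from participants who drop out and may recover some of this small loss.* If the sponsor prefers to keep both the 20% allowance and the 45 per arm, the total becomes 114, and the figure under Recruitment changes with it.
2. **Effect size.** Make the descriptions in the Sample size section and the Discussion agree, taking account of the Introduction, and state the actual basis for .60. Only the sponsor can supply that basis.

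With 108 kept, the cost is wording only, and the stated attrition cover becomes slightly less favourable. Choosing 114 means recruiting six more participants.

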The psychologists from the study will be either licensed psychologists or master students at clinical psychology and psychotherapy. They will support the participants' adherence by providing reminders using the messaging application available in the platform or via telephone, offering feedback, and monitoring the progress as well as risk for deterioration. Any crisis or any other adverse events are reported to the research team. In cases when participants forget to complete one session, the psychologists will offer reminders and send messages to participants by using platform messages and telephone messages.

Assessments

Instruments

The selected instruments have already been well established and frequently used in CBT trials for posttraumatic stress disorder in particular, as well as for other anxiety and mood disorders.

Table 2 Measurements and time assessment

Instruments	Abbreviation	Aim	Time of assessment
Clinical administered			
Posttraumatic Stress Disorder Symptom Scale Interview for DSM-5	PSS-I-5	PTSD symptoms	Pre and post treatment assessment (11) weeks
Alcohol Use Disorder Identification Test	AUDIT	Abuse and dependence of alcohol	Screening and exclusion participants with excessive drinking problems
Semi-structured clinical interview for DSM-IV	PDSQ	DSM-IV axis I severity	Pre and post treatment assessment (11) weeks
Self-report ratings			
Primary outcome			
Posttraumatic Diagnostic Scale for DSM-5	PDS-5	Severity of PTSD symptoms	Pre-treatment, middle intervention assessment (after 6 weeks), post-treatment and

			follow-up assessment (3 months)
The Posttraumatic Cognitions Inventory	PTCI	Catastrophic cognitions	Pre-treatment, middle intervention assessment (after 6 weeks), post-treatment and follow-up (3 months)
PTSD Checklist	PCL-5	Screening, monitor	Pre-treatment, every week, middle intervention assessment (after 6 weeks), post-treatment and follow-up (3 months)
Secondary outcome			
Patient health questionnaire-9	PHQ-9	Symptoms and severity of depression	Pre-treatment, every week, middle intervention assessment (after 6 weeks), post-treatment and follow-up (3 months)
General Anxiety Disorder	GAD-7	Symptoms of general anxiety disorder	Pre-treatment, every week, middle intervention assessment (after 6 weeks), post-treatment and follow-up (3 months)
The work and social adjustment scale	WSAS	Functional impairment	Pre-treatment, middle intervention assessment (after 6 weeks), post-treatment and follow-up (3 months)

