The primary outcome measures PTSD Symptom Scale - Interview for DSM-5 (PSS-I-5); Posttraumatic Diagnostic Scale for DSM-5 (PDS-5) (Foa et al., 2016); and PTSD Checklist for DSM-5 (PCL-5) (Bovin et al., 2016).

Posttraumatic Stress Disorder is assessed using the Romanian adapted version of PTSD Symptom Scale - Interview for DSM-5 (PSS-I-5). PSS-I-5 is originally a face-to-face semi-structured interview that assesses PTSD symptoms in the past months developed by Foa et al. The semi-structured interview contains 24 items that assess PTSD according to DSM-5 criteria. This traumatic event is called "trauma index" and the remaining criteria for the diagnosis are evaluated according to this event. There are 20 items which address symptoms criteria according to DSM-5 clusters: intrusions (items 1-5), avoidance (items 6-7), change in mood and cognition (items 8-14) and arousal and hyperactivity (items 15-20). These items evaluate the frequency of symptoms in the last month for the trauma index. Participants answer on a 5 point Likert scale ranging from 0 (not at all) to 4 (6 or more times a week/severe).

Symptoms are considered present when rated as 1 or higher. PSS-I-5 symptom severity is calculated by summing the items 1-20 (scores range between 0 and 80). Items 21 and 22 assess for overall distress and interference and items 23 and 24 report delayed onset and duration of symptoms, respectively. PTSD diagnosis is consistent with DSM-5 criteria and it requires presence of 1 intrusion symptom, 1 avoidance symptom, 2 cognition and mood

symptoms and 2 arousal symptoms for a period of 1 month. A significant distress or interference is also necessarily to be present (operationalized as a score of 2 or higher on either item 21 or 22).

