Posttraumatic Diagnostic Scale for DSM-5 (PDS-5). The PDS-5 (Foa et al., 2016) is a 24-item self-report questionnaire that supplements the administration of PSS-I-5. The questionnaire includes a trauma screen, followed by 20 questions corresponding to PTSD symptom according to DSM-5 criteria and offers an estimation of PTSD severity of symptoms. Participants are asked to complete the questionnaire in correspondence with “trauma index”. There are 4 clusters which assess distress, interference, onset and duration of symptom. The participants answers on a 5 point Likert scale ranging from 0 (not at all) to 4 (6 or more times a week/severe). In cases where there are multiple traumatic events, “trauma index” is evaluated as the most traumatic event, the event which currently produces the most distressing experience.

PTSD Checklist for DSM-5 (PCL-5). This scale has different versions; in our study we will use the version for the civilian population. PCL is 20 item self-report questionnaires that prompt informants to endorse the level of distress that has co-occurred according to each PTSD symptom in the previous month. PCL is used for screening, temporary diagnostic and for monitoring the symptoms on 5 point Likert scale (0 to 4) (Ruggiero, Del Ben, Scotti & Rabalais, 2003). PCL-5 total score ranges from 0 to 80, with higher score indicating greater PTSD symptom severity. PCL has excellent internal consistency (Cronbach $\alpha=.96$) and a high level of stability over time, test-retest reliability .84. Scores of 31 or 33 was demonstrated to be optimally efficient to diagnose PTSD (Bovin et al., 2016). In the study we will use PCL-5 for screening and to monitor progress and symptoms of PTSD. Participants will complete PCL-5 weekly.

Secondary outcomes

Secondary outcome measures include depressive symptoms, functional impairment, quality of life, cognitions related to trauma, stress level and other anxiety symptoms.

General mood

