We will use The Patient Feedback Questionnaire (PFQ). The questionnaire was used in a previous study which evaluates the efficacy of an iCBT program for panic attacks and it was developed by a team of researchers (Ciuca et al., 2011). The questionnaire contains 14 items which evaluate the patients' satisfaction with the platform and several other aspects (quality and utility of different components of the platform). Other items refer to giving improvement suggestions, what they like most, if they would use it again or recommend it to a friend with symptoms related to traumatic experiences. The questionnaire will be administered at post-treatment evaluation.

Drop-out reasons

In order to evaluate the reasons for drop-out we will use a questionnaire developed by Ciuca et al. The questionnaire contains 18 items and each item is considered to be a possible reason (e.g. lack of motivation, lack of time, different expectations, exacerbation of symptoms, interface is too complicated, the treatment pace is too slow or too fast, finding another treatment, getting better, important life events etc.) (Ciuca et al., 2011).

Side effects

We will evaluate negative side effects after completion of the intervention to identify any negative effects of PAXPTSD program. For this at the end of the program, participants will complete the Positive and Negative Effects of Psychotherapy Scale (PANEPS) (Moritz et al., 2018). PANEPS was evaluated in a population of individuals with depression who had completed at least one course of face-to-face psychotherapy. Factor analysis yielded four dimensions: positive effects, side effects, malpractice, and unethical conduct. Internal consistency of PANEPS range between 0.72 - 0.92 (Herzong, Lauff, Rief & Brakemeier, 2019).

Randomization

Participants who return the informed consent and meet all the required criteria are randomly allocated to one of the two conditions . The randomization process is done by a software that was developed to implement a minimization algorithm (Pocock & Simon, 1975) that assures a balanced randomization between groups with respect to certain predefined prognostic (stratification) factors. In this study, two stratification factors have been considered:

SEVERITY(4 levels according to PDS-5 screening scores; level 1: 11 to 23 points; level 2: 24 to 42 points; level 3:

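### For the interview-rated PSS-I-5, scored only before and after treatment in Table 2, the mixed model on that outcome alone is in effect a baseline-adjusted completers analysis at T3; self-report scores already collected could strengthen it

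*Protocol*

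**What the plan says.** The Statistical analysis section plans an intention-to-treat linear mixed model fitted by full information maximum likelihood, on the assumption that data are missing at random. The reason given is: "This approach was recommended since it uses all available data and can handle missing data appropriately". No distinction is drawn between outcomes, and the model terms are not listed.

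The Primary outcomes section begins: "The primary outcome measures PTSD Symptom Scale - Interview for DSM-5 (PSS-I-5", and then adds PDS-5 and PCL-5. The last two are self-reports. The Blinding section keeps the interviewers, but not the participants, unaware of allocation.

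The schedules differ by instrument:
- **PSS-I-5**: Table 2 gives "Pre and post treatment assessment (11) weeks".
- **PDS-5**: Table 2 adds a mid-treatment score and a 3-month follow-up.
- **PCL-5**: "Participants will complete PCL-5 weekly", as well as at the main visits.

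The text on interviews is not uniform. One paragraph of the Procedure section places clinician interviews at T0, T1, T3 and T4. Another, repeated in the Methods/Design section, lists interviews and self-reports together for T0 to T4, including T2, without saying which instrument is used when.

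The Drop-out reasons section offers possible reasons that include "lack of motivation, lack of time, different expectations, exacerbation of symptoms", and also improvement. The Sample size section states: "This recommended sample size has been increased to accommodate an attrition rate of 20" per cent.

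**The concern.** A likelihood-based mixed model protects against drop-out through the scores a participant leaves behind before going. PDS-5 leaves a mid-treatment score and PCL-5 a weekly series. PSS-I-5 on the Table 2 schedule leaves nothing after baseline, so someone who misses the T3 interview contributes a baseline value only. A T4 interview, if held, comes after the waiting list has been offered the programme.

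For PSS-I-5 the analysis therefore answers the intention-to-treat question only if, given baseline and arm, loss is unrelated to post-treatment severity. That can fail differently in the two arms: only the treated arm works through the modules, including exposure, while the waiting list receives nothing for 12 weeks. If treated participants who are doing badly are lost, the effect is overstated; if those who improve are lost, it is understated. PSS-I-5 is also the primary outcome least open to reporting bias in a trial whose participants know their arm.

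**Working it through.** **1. The plan's own figures.** The Sample size section says "Take this information in consideration we expected an effect size of .60" and "Based on this effect size, a power of .80 and a level alpha of 0.05", two-sided, with 45 per arm. The normal approximation is n = 2(1.960 + 0.842)² / 0.60² = 43.6, so 44; the t-test gives 44.6, so 45. Then 45 × 1.2 = 54 per arm, or 108, as stated. (Dividing by 0.8 gives 57 per arm, or 114; that is a separate matter.) A 20% loss from 54 leaves 54 × 0.8 = 43.2 per arm.

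**2. Why two visits reduce to completers.** Let X be baseline PSS-I-5, Y the T3 PSS-I-5 and g the arm. With normal data and a common baseline mean, the likelihood factors as f(X) × f(Y | X, g). A participant without Y enters only f(X), and the arm coefficient lies wholly in f(Y | X, g). So that participant adds nothing to the arm effect. Three simulated trials of 54 per arm, with 21 to 35 participants lost, confirm it: two-visit full-information estimates were −0.5022, −0.7362 and −0.4316, and completers' ANCOVA gave the same values to four decimals. If the arms have separate baseline means, those lost affect only the baseline mean to which the completers' regression is standardised.

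**3. Does the mid-treatment score carry more than baseline?** Let M be a mid-treatment self-report. On a standardised scale, the slope of Y on M given X is (r_MY − r_XM·r_XY) / (1 − r_XM²). The documents give no correlations, so three sets (r_XM, r_MY, r_XY) are assumed:
- (0.6, 0.6, 0.4): (0.60 − 0.24) / 0.64 = 0.56
- (0.6, 0.7, 0.5): (0.70 − 0.30) / 0.64 = 0.63
- (0.7, 0.8, 0.6): (0.80 − 0.42) / 0.51 = 0.75

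All are well above zero. If retention depends on M, the completers' regression on X alone is shifted within the affected arm.

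**4. Size.** From the plan: true effect 0.60 and 20% loss, applied to each arm. Assumed: the correlations above, a mid-treatment effect of 0.3 SD, and loss logistic in M with the log-odds slopes shown. Large-sample results over the three correlation sets:

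| Loss depends on mid-treatment score | Pre/post model | Bias (SD) | Mid score added |
|---|---|---|---|
| Not at all | 0.60 | 0 | 0.60 |
| Equally in both arms (slope 1.0) | 0.60 | 0 | 0.60 |
| Treated arm only, worse leave, 0.5 | 0.63–0.64 | +0.03 to +0.04 | 0.60 |
| Treated arm only, worse leave, 1.0 | 0.66–0.68 | +0.06 to +0.08 | 0.60 |
| Treated arm only, worse leave, 1.5 | 0.68–0.70 | +0.08 to +0.10 | 0.60 |
| Treated arm only, improvers leave, −1.0 | 0.52–0.54 | −0.08 to −0.06 | 0.60 |
| Opposite patterns, 1.0 and −1.0 | 0.73–0.75 | +0.13 to +0.15 | 0.60 |

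**5. Limits of the correction.** The last column is favourable by construction: loss depends only on M, and M is known for everyone. With the middle correlation set and a treated-arm slope of 1.0:
- Loss depends on the unobserved T3 score instead: pre/post 0.73, with the mid score 0.69.
- Loss depends on M, but half of those lost lack it: with the mid score, about 0.62 to 0.63.

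**6. Precision when loss is random.** At 54 per arm with 20% loss, the standard error goes from 0.197 to 0.192, from 0.190 to 0.183, and from 0.176 to 0.166. These are falls of 3%, 4% and 6% (for example 1 − 0.166/0.176 = 0.057). Adding the score costs no precision.

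**The case against.** **The protocol does not exclude auxiliary scores.** A reader might infer that the planned analysis discards the mid-treatment data. The text does not support that: it lists no model terms and does not say that each outcome is modelled alone, and a SAP could add auxiliary scores. This stands. What remains is that the protocol gives one justification for all outcomes, and on the PSS-I-5's own schedule it carries little weight.

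**The sentence is not false.** A full-information mixed model does use every value of the outcome it models, and the missing-at-random assumption is stated openly. True, but for PSS-I-5 there is nothing between baseline and T3 to use.

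**PSS-I-5 may be measured more than twice.** The strict before-and-after reading holds on Table 2. The Procedure section adds T4, so someone who misses T3 could still be interviewed later. That helps little: the waiting list is offered treatment from 3 months, and people lost before T3 may miss T4 too. The passages do conflict and need reconciling.

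**The drop-out questionnaire predicts nothing.** A reader might take its items as the sponsor's expectation of symptom-driven loss, or take symptom scores as showing why people leave. Neither follows. It is a checklist that also covers time, life events and the interface, and reasons are collected there, not by symptom scores. Stopping treatment is also not the same as missing T3, since reminders for missed assessments are planned at 7, 14, 21 and 28 days. The checklist shows only that symptom-related loss was thought possible.

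**The bias is assumed and modest.** It needs loss that differs by arm. A shift of 0.07 against a standard error of 0.19 is about a third (0.07 / 0.19 = 0.37). This is fair; but such bias is systematic, and data already planned can reduce it.

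**Conclusion.** The point holds in limited form. On the Table 2 schedule, a full-information mixed model fitted to PSS-I-5 alone is in effect a baseline-adjusted completers analysis at T3, and its missing-at-random assumption conditions only on baseline and arm. That reduction is algebraic. The size is not: under the assumed correlations and drop-out slopes, with 20% loss and a true effect of 0.60, bias is roughly 0.03 to 0.10 SD in either direction if loss follows the symptom course in one arm only, up to about 0.15 if the patterns are opposite, and about zero if the dependence is equal in both arms. Nothing in the documents shows which of these will occur.

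A stronger reading, that the trial's primary analysis as a whole is compromised, is not supported. PDS-5 and PCL-5 have scores during treatment. Binary diagnosis has its own rule, by which a missing post-treatment interview counts as still having PTSD. The change is a cheap improvement that should be made before outcome data are seen.

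**What to change.** In the Statistical analysis section, state that the T3 PSS-I-5 contrast will use a few self-report scores already collected in its missing-data model: the mid-treatment or last available PCL-5 or PDS-5, and the T3 self-report where present. Either of two methods serves:
- One joint mixed model with unstructured covariance for baseline PSS-I-5, the chosen self-reports and T3 PSS-I-5, from which the arm difference at T3 PSS-I-5 is read.
- Multiple imputation of T3 PSS-I-5 within arm from baseline PSS-I-5, those self-reports and the two minimisation factors (severity and chronicity), followed by a baseline-adjusted comparison.

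Keep the pre/post model as a sensitivity analysis, and limit the stated justification to PDS-5 and PCL-5. Say plainly that the method reduces bias, and does not remove it, when those lost have no mid-treatment score or when loss depends on the unobserved T3 score. Reconcile Table 2 with the Methods/Design and Procedure text on when the PSS-I-5 interview takes place.

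The cost is wording and some analysis time, with no new visits, data or participants. The one downside is a larger model at n = 108, which is why only a few auxiliary scores should be used.
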